5 DATA SETS TO BE ANALYSED

The following analysis sets will be used for the statistical analysis and presentation of data:

The screen set (SCR) comprises all patients who have signed the informed consent.

The Randomized Set (RS) consist of all patients who had been randomized in the study.

The safety data set (SAF) consists of all patients who have received the study medication at least once. Safety analyses will be performed based on the SAF set, and according to the treatment received.

The full analysis set (FAS) comprises all patients of the safety data set who provide the baseline value and any post-baseline value of at least one primary endpoint (6-minute walking test or daily non-sedentary daytime activity).

The per-protocol (PP) data set includes all patients of the FAS who do not have any major deviations from the protocol. Such deviations will be defined in the Data Validation Plan or similar document and in the protocol of the blind data review without knowledge of the treatment group assignment. Patients with more than 12 days between last dose administration date and 6MWT date at visit 6 will be excluded from the per-protocol (PP).

Efficacy analyses will be conducted based on FAS and PP, and according to the treatment patients were randomized to.

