6.4.2 Six minute walking test

The distance covered by the patient walking during 6 minutes will be determined and recorded at Visit 2, Visit 4, Visit 5 and Visit 6.

The assessment is performed according to the current standards (Tager et al., 2014) and will be provided as a separate manual to all sites. In brief – patients are instructed to walk down a long corridor at their own pace, attempting to cover as much distance as possible within 6 minutes. At the end of the 6 minute duration, the walked distance is calculated and recorded along with the symptoms experienced by the patient. It is crucial that patients are allowed to

rest, before the test is performed – therefore the 6-minute walking test should be done as the last assessment at the respective visits.

[figure not shown]

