9.1 Analysis sets

Three analysis data sets will be defined. The safety data set (SAF) consists of all patients who have received the study medication at least once. The full analysis set (FAS) comprises all patients of the safety data set who provide the baseline value and any post-baseline value of at least one primary endpoint (6-minute walking test or daily non-sedentary daytime activity). The per-protocol (PP) data set includes all patients of the FAS who do not have any major deviations from the protocol. Such deviations will be defined in the Data Validation Plan or similar document and in the protocol of the blind data review without knowledge of the treatment group assignment.

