9.4.3 Handling of missing values/censoring/discontinuations

For patients who do not have the baseline values or patients who drop out prematurely and/or do not have a valid measurement in mean daily non-sedentary daytime activity between weeks 10-12, a Multiple Imputation (MI) method will be used for the primary analysis.

In case of qualitative (e.g., increased level of non-sedentary daytime physical activity) or semi-quantitative (e.g., PGA) efficacy variables, missing Week 12 values of patients previously dropped out due to hospitalization or death will be substituted by the worst value possible for the respective variable (e.g., increased level of non-sedentary daytime physical activity="No", PGA="much worse").

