4 OVERALL STUDY DESIGN

4.1 Overview of Study Design

This is an international (European), randomized, actively controlled, double-blind, double-dummy, interventional study with prospective data collection. The study comprises 6 visits over 14 weeks. Adult patients with symptomatic HFREF (NYHA classes II or III/IV at a 1:1 ratio) managed in an ambulatory setting (i.e. by primary care physicians, office based cardiologists, HF outpatient clinics) will be randomized in a 1:1 allocation to receive sacubitril/valsartan or enalapril during the double-blind period. Actigraphy will be performed during the entire duration of the study by means of a wrist-worn accelerometry device; the device will be worn continuously for two weeks prior to randomization in order to obtain an individual baseline for each patient, and throughout the treatment period of the study (12 weeks). Figure 4-1 depicts the study design along with the treatment and visit schedule.

Figure 4-1 Study design

¹⁻² sacubitril/valsartan or enalapril (double-blind study drugs) will be given at dose levels (up-titration) depending on pre-study ACEI/ARB doses.

³Pre-study ACEI and/or ARB are replaced by study medication after Visit 2. Therefore washout period (WO) of 36 hours is required; it should start 12 hours before Visit 2 (randomization); the first study treatment intake should be 24 hours after Visit 2. All other HF background and CV medications (e.g. beta blockers, MRAs etc.) and symptomatic treatment (e.g. diuretics) the patient has been taking should remain unchanged throughout the study, if possible and medically justified in the judgement of the investigator.

"Background HF medication per local practice": patients must be on stable HF treatment regimen for at least 4 weeks prior Visit 1. After Visit 1, patients shall retain their pre-study HF treatment for another 2 weeks (week -2 to week 0) for baseline actigraphy recording.

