For the analyses of further secondary and of the exploratory endpoints referring to data at 'end of study' the same algorithm will be applied to create an extra LOCF visit next to the usual Week 12 visit. This additional 'end of study' measure constitutes a conservative approach in handling of missing data and ensures much as possible unbiased and comparable efficacy results.

In case of qualitative (e.g., increased level of non-sedentary daytime physical activity) or semi-quantitative (e.g., PGA) efficacy variables, missing Week 12 values of patients previously dropped out due to hospitalization or death will be substituted by the worst value possible for the respective variable (e.g., increased level of non-sedentary daytime physical activity="No", PGA="much worse").

In the event that any date for Adverse Events is incomplete after Data Management processing and this date needs to be used for a calculation, the following will be assigned for the missing date:

- if no field is available: no imputation will be performed
- if only the year is available:
 - Onset date: day "01" and month of "January" or first dose administration date, whatever occurs after will be imputed
 - End date: day "31" and month of "December" or EOS date, whatever occurs before will be imputed
- if the month and year are available:
 - Onset date: day "01" will be imputed
 - End date: "last day of the month" will be imputed

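### The full analysis set leaves out treated patients with no retrievable post-baseline value, so the plan's worst-value rule cannot score the earliest deaths and hospitalisation drop-outs in the week-12 responder and PGA endpoints

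*SAP*

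**What the plan says.** Protocol 9.1 and SAP 5 define the FAS alike. It takes treated patients "who provide the baseline value and any post-baseline value of at least one primary endpoint (6-minute walking test or daily non-sedentary daytime activity"). Either co-primary is enough: the 6-minute walk test (6MWT) or non-sedentary daytime activity.

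The SAP states which sets carry efficacy: "Efficacy analyses will be conducted based on FAS and PP, and according to the treatment patients were randomized to". It also defines a wider set ("The Randomized Set (RS) consist of all patients who had been randomized in the study"), but no efficacy table listed in SAP 8.1 uses it.

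Two missing-data rules matter here, both in Protocol 9.4.3 and SAP 6.6:

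- For qualitative and semi-quantitative efficacy variables, "missing Week 12 values of patients previously dropped out due to hospitalization or death will be substituted by the worst value possible". The examples are No for the activity responder and much worse for PGA.
- For the activity co-primary, multiple imputation (MI) is used. The rule opens "For patients who do not have the baseline values or patients who drop out prematurely", and SAP 6.3.7 runs it in the FAS.

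Neither rule excepts early drop-outs. No imputation is written for the 6MWT co-primary.

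On timing, the 6MWT "will be determined and recorded at Visit 2, Visit 4, Visit 5 and Visit 6", so the first post-baseline test is due at week 4. Actigraphy is worn for two weeks before randomisation "and throughout the treatment period of the study (12 weeks"). Its scheduled post-baseline downloads are at Visit 4 and Visit 6, and Table 6-1 also marks a download at an unscheduled visit.

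**The concern.** Membership of the FAS depends on something measured after randomisation. The patients it removes are treated patients with no post-baseline 6MWT and no retrievable post-baseline actigraphy. These are mainly early deaths where the device is not read, and early withdrawals or losses who attend neither the early end-of-study (EOS) visit nor an unscheduled visit. Weeks 0 to 4 are the titration period, so such losses could differ by arm.

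For deaths and hospitalisation drop-outs in this group, the set definition works against the missing-data rule. A patient who is tested at Visit 4 and dies in week 6 is a responder failure. A patient who dies in week 2 with no device reading is not in the denominator. The documents give no reason for treating the two differently. The activity MI cannot reach any patient in this group either, whatever the reason for loss.

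At stake are the week-12 responder comparisons (6MWT gain of at least 30 m, with its two baseline-distance subsets, and activity gain of at least 10%) and PGA. No planned analysis shows how far they depend on the exclusion.

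**Working it through.** **Planning figures.** The exact two-sample t-test at two-sided 5% and 90% power gives 258.4, rounded up to 259 per arm, for 20 min/day with SD 70. It gives 223.9, rounded up to 224, for 35 m with SD 114. Both match Protocol 9.8. The margin is (300 − 259)/300 = 41/300 = 13.7%, described as an allowance for non-eligible patients. No rate of early death, hospitalisation or drop-out is given, so every loss rate below is an assumption.

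**Power.** Using power = Φ(δ/(σ√(2/n)) − 1.96) with n = 300(1 − loss):

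| Loss per arm | n | Activity | 6MWT |
|---|---|---|---|
| 1% | 297 | 93.6% | 96.3% |
| 2% | 294 | 93.4% | 96.1% |
| 5% | 285 | 92.7% | 95.6% |
| 10% | 270 | 91.3% | 94.6% |

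These are for each endpoint alone at 5%. Power is not the issue.

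**Responder endpoints.** Let r1 and r0 be the FAS responder rates on sacubitril/valsartan and enalapril. Let q1 and q0 be the shares of treated patients left out of the FAS after early death or hospitalisation drop-out.

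- Difference in the current FAS: r1 − r0.
- Difference in all treated patients, with these losses scored as failures: r1(1 − q1) − r0(1 − q0).
- Shift (first minus second): r1q1 − r0q0.
- Standard error of a difference with 300 per arm: √(2 × 0.25/300) = 4.1 points.

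Example: r1 = 52%, r0 = 40%, q1 = 5%, q0 = 2%. The FAS difference is 12.0 points. The all-treated difference is 0.52 × 0.95 − 0.40 × 0.98 = 0.494 − 0.392 = 10.2 points. The shift is 1.8 points, or 1.8/4.08 = 0.44 SE.

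| q1 / q0 | Shift (points), equal rates 30–50% | Shift (points), r1 45–52%, r0 40% | Last column in SE |
|---|---|---|---|
| 1% / 1% | 0 | 0.05 to 0.12 | 0.01 to 0.03 |
| 2% / 1% | 0.3 to 0.5 | 0.50 to 0.64 | 0.12 to 0.16 |
| 3% / 1% | 0.6 to 1.0 | 0.95 to 1.16 | 0.23 to 0.28 |
| 5% / 2% | 0.9 to 1.5 | 1.45 to 1.80 | 0.36 to 0.44 |
| 1% / 2% | −0.3 to −0.5 | −0.28 to −0.35 | −0.07 to −0.09 |
| 1% / 3% | −0.6 to −1.0 | −0.68 to −0.75 | −0.17 to −0.18 |
| 2% / 5% | −0.9 to −1.5 | −0.96 to −1.10 | −0.24 to −0.27 |

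A positive shift means the FAS flatters sacubitril/valsartan; a negative one means it understates it.

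**Co-primaries.** For the 6MWT, an excluded patient has no week-12 value and the plan imputes none, so enlarging the set leaves the ANCOVA unchanged. For activity, leaving patients out shifts the difference by (q1 − q0) × (gap between excluded and included patients). With an assumed 2-point difference and an assumed gap of 50 min/day, that is 0.02 × 50 = 1 min/day, against a planned difference of 20. MI that can use only baseline information for these patients would recover little even of that.

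**The case against.** The strongest reply is that few patients are affected. Actigraphy is recorded from randomisation, so a patient lost in week 2 whose device is read can enter the FAS. Protocol 6 brings the EOS visit forward for anyone who leaves the study early, with all assessments; Table 6-1 marks both the 6MWT and the download at that visit. Patients who stop drug should return the device at the unscheduled visit. Protocol 5.5.5 and 5.6.2 keep them in follow-up, and any later value qualifies. All of this stands. A reader might infer from the week-4 walk test that everyone hospitalised or taken off drug during titration drops out of the FAS. The documents do not support that: the group is confined to patients with neither a post-baseline 6MWT nor a retrievable recording.

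A second reply is that the affected endpoints are exploratory under Protocol 9.5.1, and that exclusions will be visible in Table 14.1-1 and Listing 16.2.3-1.1. That also stands, and it limits the weight of the point. But those outputs disclose exclusions without showing their effect on the result.

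Third, the worst-value rule covers only drop-out through hospitalisation or death, so for other early losses it has nothing to apply. That is right; for them only the activity MI is out of reach.

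**Conclusion.** The point holds in a limited form. The FAS rule selects on a post-randomisation measurement and stops the plan's own worst-value rule from scoring the earliest deaths and hospitalisation drop-outs that leave no data. It matters mainly for the exploratory week-12 responder and PGA endpoints.

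The size rests wholly on assumed loss and responder rates: about 0.3 to 1.8 percentage points for a loss difference of 1 to 3 points, at most about 0.44 SE, and about 0.1 point or less with equal 1% loss.

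Three stronger readings are not supported:

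- That the confirmatory 6MWT result is biased by skipping an imputation rule. None is written for it.
- That the exclusion favours sacubitril/valsartan. The sign follows whichever arm loses more, which the documents do not tell us.
- That 13.7% caps the loss. It is a recruitment margin and bounds nothing.

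This is a cheap improvement in consistency; it does not threaten the primary analyses.

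**What to change.** In Protocol 9.1 and SAP 5, add an efficacy set of all randomised patients who took study drug (or give the existing Randomized Set this role), analysed as randomised, with no post-baseline requirement. In that set:

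- Analyse the week-12 responder endpoints and PGA, applying the existing worst-value rule to drop-out through hospitalisation or death.
- Repeat the activity co-primary with the existing MI, as a sensitivity analysis.

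Keep the current FAS results alongside. Because the FAS stays in use, state how much recording counts as a post-baseline activity value, which neither document does, and report exclusions from the FAS by arm and reason.

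The cost is analysis-set wording, one repeated table run, and a few more imputed or worst-value scores. No new data are needed. Amendment 4 says the last patient visit has taken place, but SAP 6.2 settles set membership at a blind review before database closure, so on the documents' own timetable the change can be made blind.

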6 STATISTICAL AND ANALYTICAL PLANS

The planned tables and listings are presented in Appendix 1.

6.1 Changes in the Planned Analyses

Following sleep parameters are not possible to be collected as defined in protocol

- Mean daily sleep efficiency
- Mean daily time in bed
- Actual sleep time
- Actual wake time
- Sleep latency.
- Mean daily sleep fragmentation, defined as the sum percent mobile time and percent immobile bouts of ≤ 1 min duration

In order to give more information about the actigraphy data and the evolution of the patients during the study, new variables (Non Parametric Circadian Rhythm Analysis (NPCRA)) will be add to the analysis.

Non Parametric Circadian Rhythm Analysis (NPCRA): Long-term recordings of activity levels show a rhythmic pattern with alternating high levels of activity during the day and low levels of activity during the night. Such alternating patterns are known as circadian rhythms, from the Latin words 'circa' (approximately) and 'dies' (day). These rhythms are not only present in activity levels but also in hormone levels, body temperature and virtually all measurable biological events, including molecular, physiological, behavioral and cognitive phenomena.

The specific characteristics of circadian rhythms may be of interest to researchers and clinicians, and thus need to be quantified. Many circadian rhythms resemble a cosine wave, and indeed there is a long tradition in circadian rhythm research to fit a cosine curve to the data, and to use the mesor (mean), amplitude and phase of the fitted curve as variables of interest. One may for example be interested whether a patient group differs from a control group on their average mesor, amplitude or phase. The method is known as Cosinor-analysis.

Activity data, however, seldom resemble a cosine wave, and it is consequently not appropriate to apply Cosinor-analysis in order to obtain valid parameters describing the rhythms. Therefore, a number of alternative quantification methods have been developed. These methods do not suppose the rhythm to have a cosine-like shape. Details on the mathematics and usefulness of the measures can be found in e.g. (Van Someren et al., 1996; Van Someren et al., 1997a; Van Someren et al., 1997b; Van Someren et al., 1998; Van Someren et al., 1999).

NPCRA Variables – Interdaily Stability (IS)

A first nonparametric variable is the Interdaily Stability (IS). This variable quantifies the degree of resemblance between the activity patterns on individual days. If, for example, a subject has a very rigid schedule of getting up in the morning every day at the same time, and shows activity and rest periods every day at the same time, this will result in a high Interdaily Stability. The measure theoretically ranges from 0 to 1, and may typically be about 0.6. A higher value indicates a more stable rhythm. The variable has shown to be sensitive to rhythm changes in Alzheimer's dementia: whereas normal human aging is associated with rather regular or even rigid daily activity schedules, demented elderly may show very different profiles from day to day.

NPCRA Variables – Intradaily Variability (IV)

Another nonparametric variable is the Intradaily Variability (IV). This variable quantifies the fragmentation of periods of rest (or sleep) and activity (or wakefulness). Healthy subjects usually show one prolonged activity period and one prolonged rest period in every 24-hour cycle. Under certain conditions, as high age and Alzheimer's dementia, the periods of rest and activity may become shorter, or fragmented, for example due to naps during the day and periods of nocturnal restlessness. The measure theoretically ranges from 0 to 2, with higher values indicating a more fragmented rhythm, and typically is below 1.

NPCRA Variables – L5 and M10

As mentioned before, it is not appropriate to fit a cosine wave to activity data. However, one may still want to have an indication of the trough level, peak level, amplitude, and phase of the rhythm. Useful nonparametric variables have been developed in order to quantify these rhythm phenomena. They are all based on an average 24-hour curve, calculated by overlaying all available 24-hour periods. In this 24-hour average curve, the sequence of the five least active hours is denoted 'L5'. The average activity during these five hours gives an indication of the trough or nadir of the rhythm, i.e. how restful and regular the rest (sleep) periods are. The time of onset of the sequence marks the phase of the onset of the most restful five hours.

In a similar way, the sequence of the ten most active hours is denoted 'M10'. The average activity during these ten hours gives an indication the peak of the rhythm, i.e. of how active and regular the activity (wake) periods are. The time of onset of the sequence marks the phase of the onset of the most active ten hours.

NPCRA Variables – Amplitude

The difference between the average activity level during M10 and the average activity level during L5 gives an indication of the amplitude of the rhythm, and is denoted as 'AMP'. This measure is sensitive to the overall level of activity, which is not always wanted. For example, if one measures activity on the trunk instead of the wrist, the activity level will drop both during the day and during the night, resulting in a 'smaller' amplitude.

As a correction for the offset in sensitivity to movements, one may prefer to use the relative amplitude (RA), which is calculated by dividing AMP by the sum of L5 and M10. The measure theoretically ranges from 0 to 1, with higher values indicating a rhythm of higher amplitude.

6.2 Blind Review

The blind review meeting will be held before database closure and before breaking the blind to make final assessments of which patients should be included in the analysis sets and other decisions regarding the statistical analysis.

Protocol deviations observed and documented during the study (Protocol deviation log from the study site and observed during the data validation) will be listed in Section 16 of the CSR. Patients with major protocol deviations will be excluded from the PP population.

All relevant listings and tables prepared for the data review meeting will be verified for consistency and correctness by the study data manager and the statistician [REDACTED] and the Sponsor before the database is locked.

Apart from the data review meeting after LPLV, other data review meetings during the study may be done if appropriate to review protocol deviations and identify trends or recurrent queries within or across sites/countries.

6.3 Hypotheses and Statistical Methods

6.3.1 Definitions

Study baseline

For all objectives/endpoints assessed by means of actigraphy, the baseline value is obtained over a period of two weeks prior to randomization, i.e. week -2 to week 0.

Parameters collected in both Visit 1 and Visit 2: for assessments (Vital signs, NYHA class, [REDACTED] and laboratory evaluations) the last non-missing assessment prior to the first dose will be considered as the baseline value in order to calculate the changes between baseline visit and following visits.

Actigraphy

Actigraphy is a non-invasive method of monitoring human physical activity patterns. Actigraphy will be performed in this study by means of a wrist-worn device that collects data on activity (by means of tri-axial accelerometry). The device (MotionWatch8[®], CamNtech, Cambridge, UK) collects the data on movement continuously in 30-second bins. The device is lightweight and waterproof and worn on the wrist of the non-dominant arm continuously (24 hours/day) for the entire study duration. Based on accelerometry for each 30-second bin, activity counts for each minute of each day are generated. Higher counts reflect a higher level of activity. For an elderly population, cut-off values for activity counts per minute defining the intensity of physical activity have previously been defined ([Landry, Falck et al. 2015](#)). These cut-off values will be used to define sedentary, light and moderate to vigorous activity counts for each minute the device is worn. Sedentary activity is defined as < 178.5 activity counts per minute; light activity as 178.5 – 565.5 activity counts/minute and > 565.5 activity counts/minute define moderate to vigorous physical activity (see also [Figure 3-1](#)). The time patients spend in a given activity intensity category will be recorded and represents the basis for all endpoints that are derived from actigraphy. Where appropriate, activity data will be integrated over 2-week intervals (i.e. baseline non-sedentary physical daytime activity is the mean time per day the patient spent in non-sedentary activity during the daytime during the 14 days of baseline recording (week -2 to week 0).

M6min

M6min is a parameter derived by validated algorithms of the software that will be used to pre-process actigraphy data. The parameter reflects the peak 6 minutes of physical activity. The mean daily M6min will be calculated over 14 day epochs.

Actigraphy measurements

All variables needed for actigraphy objectives will be calculated using CamNtech Motionware 1.2.18 software or latest version.

- Mean daily non-sedentary daytime activity
- Mean daily light and moderate-to-vigorous non-sedentary daytime physical activity
- Total weekly time spent in non-sedentary daytime physical activity.
- Total weekly time spent in light non-sedentary daytime physical activity.
- Total weekly time spent in moderate-to-vigorous non-sedentary daytime physical activity
- M6min
- Interdaily Stability (IS)
- Intradaily Variability (IV)
- L5 average
- M10 average
- Relative Amplitude

Six minute walking test

The distance covered by the patient walking during 6 minutes will be determined and recorded at Visit 2, Visit 4, Visit 5 and Visit 6.

The assessment is performed according to the current standards ([Tager, Hanholz et al. 2014](#)) and will be provided as a separate manual to all sites. In brief – patients are instructed

to walk down a long corridor at their own pace, attempting to cover as much distance as possible within 6 minutes. At the end of the 6 minute duration, the walked distance is calculated and recorded along with the symptoms experienced by the patient. It is crucial that patients are allowed to rest, before the test is performed – therefore the 6-minute walking test should be done as the last assessment at the respective visits.

[figure not shown]
Patient Global Assessment (PGA)

The Patient Global Assessment (PGA) is a self-reported tool to assess the patients' subjective rating of their disease activity widely used in HF research and other indications. It has been shown that the PGA responses of CHF patients correlate the patients' functional capacity assessed by means of the 6-minute walk test ([Cooper, Anker et al. 2016](#)).

The patients are asked to report functioning or response to an intervention by rating their current condition compared to their pre-intervention condition on a numerical scale:

- 1) much improved
- 2) moderately improved
- 3) a little improved
- 4) unchanged
- 5) a little worse
- 6) moderately worse or
- 7) much worse.

This self-assessment will be completed by the patients in a quiet environment, before any study assessment or drug dispensing at Visit 4, Visit 5 and Visit 6.

